4.2.2.1 Non-responder imputation

For binary endpoints, the non-responder imputation (NRI) analysis, also described above as the composite estimand, will consider the following subjects as “non-responders” for the timepoint of interest:

- Subjects with missing data at the time point of interest. In the case of ACR50, non-response is imputed if ACR50 cannot be derived (ie: derived as “missing”) based on available ACR components ([Section 8.1.1](#))
- Subjects who remained in the study at the timepoint of interest but discontinuing study treatment before the timepoint of interest (data after IE)
- Subjects with missing Baseline value (for composite or non-composite binary variables based on change(s) from Baseline of continuous endpoint(s)).

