4.2.2.4 Tipping Point analysis

Tipping point analyses will also be implemented as a supportive analysis for the primary efficacy endpoint. This analysis will be performed only for the subjects randomized to Placebo and BKZ.

The objective of the tipping point analyses is to identify assumptions about the missing data under which the conclusions from the main analysis change (ie: under which there is no longer

evidence of a treatment effect). These tipping point analyses will only be performed if the primary efficacy analysis results in a statistically significant treatment effect ($p < 0.05$).

As a first step, the worst-case scenario will be evaluated. Specifically, all BKZ randomized subjects with a missing ACR50 at Week 16 (or non-missing ACR50 after study treatment discontinuation) will be imputed as non-responders, while all placebo-randomized subjects with a missing ACR50 at Week 16 will be imputed as responders. While there is little justification for such an approach, it makes the most putative assumption possible against a BKZ treatment effect. After applying this imputation approach, a logistic regression model consistent with the one described for the primary analysis will be applied. If the p-value for the OR of BKZ versus placebo is < 0.05 , then no further tipping point analyses are needed.

If this analysis based on the worst-case scenario results in a $p > 0.05$, then additional tipping point analyses will be performed. In practice, it implies different delta adjustments will be made to the assumed responses on the missing data (where missing values include observations after the IE date and any other missing values) in each treatment group independently with various degrees of plausibility with the goal to find for each treatment group the “tipping point” that will significantly reverse the primary result which yielded a $p < 0.05$. These delta adjustments will be done on each component of ACR50 as follows:

- Step 1: The same MCMC method described in [Section 4.2.2.2](#) will be implemented for non-monotone (intermittent) missing pattern values, using the same imputation model. This will be based on 100 imputations.
- Step 2: Based on the datasets obtained in Step 1, a monotone regression model will be applied (using the same imputation model as in Step 1) and as described in [Section 4.2.2.2](#). This will be based on 1 imputation.
- Step 3: Imputed values will be shifted using a delta adjustment independently in each treatment group.

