8 EFFICACY ANALYSES

8.1 Statistical analysis of the primary efficacy variable

8.1.1 Derivation of ACR50 response

The ACR50 response at Week 16 is the primary efficacy variable.

This is a composite endpoint that represents at least 50% improvement from Baseline at Week 16 for each of the following:

- TJC (based on 68 joints),
- SJC (based on 66 joints),
- At least 3 of the 5 remaining core set measures:
 - PGA-PsA
 - PhGA-PsA
 - PtAAP
 - HAQ-DI
 - hs-CRP.

Prior to deriving ACR50, the percent of change for each component will be calculated as:

$$\text{Percent improvement from Baseline} = 100 \times \frac{\text{Baseline Value} - \text{Week 16 value}}{\text{Baseline Value}}$$

As the ACR response is based on 7 different component scores, it is necessary to consider various data scenarios that could impact the calculation of ACR response. The rules described here are applicable in the context of the calculation of ACR response and may differ from the rules applied for calculating and summarizing the components individually (some values may need to be imputed for component analysis but are not required here to evaluate the ACR response)

The following rules will be applied prior to invoking any imputation analysis at the variable level:

- If a subject has a component value that is equal to 0 at Baseline and the post-Baseline value is ≥ 0 , then the percent improvement for that component will be treated as 0 for purposes of ACR response calculations.
- If a subject has a component value that is missing at Baseline, then the percentage of improvement for that component will be treated as missing for purposes of ACR response calculations.

Observed data will be used to calculate ACR response where possible. In case of partial missing data where an observed response may be calculated, imputed data will not change the result.

To address possible missing data in ACR components, ACR50 will be derived as below:

- Positive response on ACR50:

- Improvement at Week 16 of at least 50% from Baseline on SJC and TJC and at least 3 out of the 5 remaining ACR components (regardless of whether the 2 remaining components are missing or not).
- Negative response on ACR50:
 - No improvement at Week 16 of at least 50% from Baseline on SJC (regardless of whether the remaining components are missing or not).
 - No improvement at Week 16 of at least 50% from Baseline on TJC (regardless of whether the remaining components are missing or not).

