 - No improvement for at least 3 out of the 5 following ACR components (PGA-PsA, PhGA-PsA, PtAAP, HAQ-DI, hs-CRP) regardless of whether the remaining components are missing or not.
- Missing ACR50 response:
 - For all other situations that are not specified above.

For the OC analysis ([Section 8.1.4.6](#)): if a given visit date falls after the treatment discontinuation date, the endpoint at this visit and all subsequent visits (whether the data were observed or not) will be derived but reported as missing.

For the MI analysis ([Section 8.1.4.3](#)): If a given visit date falls after the treatment discontinuation date, the endpoint at this visit and all subsequent visits (whether the data were observed or not) will be imputed. Responses falling after an IE (defined as treatment discontinuation due to AE or lack of efficacy for the modified composite estimand) will be set to non-response.

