8.1.4.6 Analysis on Observed cases

An OC analysis will additionally be conducted, where only observed data for subjects who are still on the randomized treatment at Week 16 are included. Subjects with missing data at Week 16 or who have prematurely discontinued study treatment prior to Week 16 will be treated as missing and missing data will not be replaced.

The following 4 attributes describe the estimand that will be used to define the treatment effect of interest for the OC analysis:

- Population = Subjects enrolled according to the protocol-specified inclusion/exclusion criteria and randomized to IMP.
- Subject-level outcome = ACR50 at Week 16 while on randomized treatment.

- IE handling = A "while on randomized treatment" strategy will be implemented.
- Population-level summary measure = Conditional OR comparing BKZ to placebo.

The same analysis model as used for the primary efficacy analysis will be conducted on the RS.

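### The third rule for a negative ACR50 lacks the 50% threshold, so, coded as written, some non-responders with complete data are classed as missing

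*SAP*

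**What the plan says.** SAP Section 8.1.1 first defines ACR50 at Week 16 as at least 50% improvement from Baseline in TJC, in SJC and in at least 3 of the 5 other core measures (PGA-PsA, PhGA-PsA, PtAAP, HAQ-DI, hs-CRP). It then sets out derivation rules to deal with missing components:

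- Positive: "Improvement at Week 16 of at least 50% from Baseline on SJC and TJC and at least 3 out of the 5 remaining ACR components".
- Negative, first rule: "No improvement at Week 16 of at least 50% from Baseline on SJC".
- Negative, second rule: "No improvement at Week 16 of at least 50% from Baseline on TJC".
- Negative, third rule: "No improvement for at least 3 out of the 5 following ACR components", with no percentage.
- Missing: "For all other situations that are not specified above".

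Three other places decide what happens to a missing ACR50:

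- Section 4.2.2.1, the primary method: "In the case of ACR50, non-response is imputed if ACR50 cannot be derived".
- Section 8.1.4.6, observed cases (OC): subjects with missing Week 16 data "will be treated as missing and missing data will not be replaced".
- Section 4.2.2.4, worst-case tipping-point step: "all placebo-randomized subjects with a missing ACR50 at Week 16 will be imputed as responders", while BKZ subjects with a missing ACR50 are set to non-response.

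Sections 8.2.1.9 and 8.3.1.2 derive ACR20 and ACR70 from the same rules with other percentages.

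**The concern.** The three negative rules should together be the complement of the positive rule when all components are observed. They are not. The third rule asks for an absence of improvement, whereas the definition only requires that the 50% mark is not reached. Subjects between those two limits are caught by neither rule, so they fall into the residual category and are called missing although nothing is missing.

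This is the derivation of the primary endpoint. If the rules are programmed as written, true non-responders drop out of the OC denominator. In the worst-case tipping-point step, true placebo non-responders become responders. A program written from the definition and one written from the rules would give different results in analyses that are meant to test the robustness of the primary result.

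**Working it through.** **Step 1: one subject.** SJC and TJC improve by 60%, two other measures by 60%, three by 30%; all seven are observed.
- Definition: 2 of 5 other measures reach 50%, and 3 are needed, so this is a non-responder.
- Positive rule: not met (2 of 5).
- Negative rules 1 and 2: not met (both joint counts reach 50%).
- Negative rule 3 as written: not met (every measure improved).
- Result as written: missing.

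**Step 2: all complete-data patterns.** Take both joint criteria as met. Give each of the 5 other measures one of three states: improved by at least 50% (H), improved by less than 50% (P), or not improved (N). There are 3^5 = 243 patterns.
- Positive (at least 3 H): 10×4 + 5×2 + 1 = 51.
- Negative as written (at least 3 N): 51 by the same count.
- Missing as written: 243 − 51 − 51 = 141.
- With the 50% threshold in rule 3 (at least 3 of N or P): 51 positive, 192 negative, 0 missing.

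All 141 patterns move from missing to negative, and no positive changes. Allowing a fourth state, component missing, gives 4^5 = 1024 patterns. As written, 106 are positive, 106 negative and 812 missing. With the threshold, 106 are positive, 512 negative and 406 missing, and the 406 reclassified patterns all become negative. These are counts of patterns, not probabilities.

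**Step 3: effect on OC rates.** Inputs are the planning rates in Section 2.4.1: BKZ 43.8%, placebo 16%, difference 27.8 points. The odds ratio is (0.438/0.562)/(0.16/0.84) = 4.09, which agrees with the SAP. Let f be the share of all subjects in an arm moved from non-responder to missing. The SAP does not give f, so the values below are assumptions, with no other missing data. The OC rate is p/(1 − f); at f = 10%, 0.438/0.90 = 0.487 and 0.16/0.90 = 0.178.

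| f, BKZ / placebo | BKZ | Placebo | Difference (points) | Odds ratio |
|---|---|---|---|---|
| 0 / 0 | 43.8% | 16.0% | 27.8 | 4.09 |
| 5% / 5% | 46.1% | 16.8% | 29.3 | 4.22 |
| 10% / 10% | 48.7% | 17.8% | 30.9 | 4.38 |
| 20% / 20% | 54.8% | 20.0% | 34.8 | 4.84 |
| 10% / 5% | 48.7% | 16.8% | 31.8 | 4.68 |
| 5% / 10% | 46.1% | 17.8% | 28.3 | 3.96 |

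Here f is a share of all subjects. Removing 10% of non-responders only would give 0.438/(1 − 0.0562) = 46.4% and 0.16/(1 − 0.084) = 17.5%.

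**Step 4: worst-case tipping-point step.** The affected BKZ subjects stay non-responders, so BKZ remains at 43.8%. Placebo becomes 16% + f: 21%, 26% or 36% for f = 5%, 10% or 20%. Here the error works against BKZ.

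**Step 5: primary analysis.** A missing ACR50 is counted as non-response, so the rates stay at 43.8% and 16.0% for any f.

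**The case against.** The strongest reply is that the definition at the head of Section 8.1.1 already settles complete records. The rules that follow are introduced as a way to handle missing components, and the section says that observed data are to be used where possible. The two parallel rules make the intended 50% obvious, and a careful programmer would supply it. That makes correct coding likely, but it does not remove the conflict: the same section says that ACR50 is derived by these rules, and no other section restores the threshold. The error arises only if the rules are coded literally.

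Four stronger readings are tempting, and the document does not support them:

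- **The treatment effect is inflated in favour of BKZ.** Rates rise in any arm with affected subjects, but the OC summary measure is the odds ratio. It depends on f in each arm and can fall, as in the last row of the table.
- **A definite size can be given.** The SAP gives no joint distribution of the seven components, so any single value of f is an assumption.
- **The multiple-imputation analyses lose subjects too.** This is arguable only. Section 4.2.2.2 derives the binary endpoint after every component has been imputed, and Section 8.1.4.3 refers back to Section 8.1.1 for partially missing data. Whether the residual category is applied to a completed record is not stated.
- **Every subject with partial improvement becomes missing.** Subjects with at least 3 of the 5 measures not improved at all are negative even under the literal rule.

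**Conclusion.** The rule is wrong as written and contradicts the definition in the same section. Coded literally, it classes some fully observed non-responders as missing. The primary NRI result is unaffected. The certain consequences of literal coding are higher OC response rates in any arm with such subjects, and such placebo subjects counted as responders in the worst-case tipping-point step. ACR20 and ACR70 inherit the gap. Its size is unknown: under the assumed range of 5% to 20% of all subjects in both arms, the OC difference on planning rates would be 29.3 to 34.8 points instead of 27.8. The direction of the effect on the odds ratio is not established. The text should be corrected because it governs the primary endpoint and its supportive analyses, even though the primary conclusion does not depend on it.

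**What to change.** In the third negative rule of Section 8.1.1, insert the threshold that the SJC and TJC rules carry: failure to reach 50% improvement from Baseline at Week 16 in at least 3 of the 5 listed measures, whether or not the remaining components are missing. State in Sections 8.2.1.9 and 8.3.1.2 that the threshold in all three negative rules becomes 20% for ACR20 and 70% for ACR70.

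The cost is one line of SAP wording and a program check that no record with all seven components observed has a missing ACR status. No positive response changes, and the primary result stays as it is. If existing programs follow the literal rule, the OC and worst-case tipping-point outputs need a rerun.

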8.1.1.1 Derivation of tender joint count (TJC) and swollen joint count (SJC)

Tender and swollen joints are assessed based on the 68 and 66 joints for tenderness and swelling, respectively. The 68/66 joints that are assessed are:

- Upper body (6): bilateral temporomandibular, sternoclavicular, and acromioclavicular joints
- Upper extremity (34): bilateral shoulders, elbows, wrists (includes radiocarpal, carpal and carpometacarpal joints considered as 1 unit), metacarpophalangeals (I, II, III, IV, V), thumb interphalangeals, proximal interphalangeals (II, III, IV, V), distal interphalangeals (II, III, IV, V)
- Lower extremity (28): bilateral hips, knees, ankles, tarsi (includes subtalar, transverse tarsal, and tarsometatarsal joints considered as 1 unit), metatarsalphalangeals (I, II, III, IV, V), great toe interphalangeals, and proximal interphalangeals (II, III, IV, V).

The assessments on swelling exclude the hips.

Each of the joints can be graded as follows by the assessor:

- Permanently not assessable
- Temporarily not assessable
- Asymptomatic
- Tender only

- Swollen only
- Tender and swollen

Permanently non-evaluable joints will be considered missing for both tender and swollen joint counts at the visit at which the grading was recorded and all subsequent visits. The asymptomatic joints will be included in the joint count analysis with scores of 0.

For the statistical analysis, swelling and tenderness are each graded on a 2-point scale as described below:

Table 8-1: Swelling and Tenderness grading

Present	Tenderness response (68)	Swelling response (66)
No (0)	Not tender	None
Yes (1)	Positive response to questioning (tender), spontaneous response elicited (tender and winced) or withdrawal by subject on examination (tender, winced, and withdrew).	Detectable synovial thickening with or without loss of bony contours, or bulging synovial proliferation with or without cystic characteristics.

The joint graded by the assessor will then have its grade mapped as follows:

- The “Tender only” joints will correspond to a tenderness response of 1, and a swollen response of 0.
- The “Swollen only” joints will correspond to a swollen response of 1, and a tenderness response of 0.
- The “Tender and swollen” joints will correspond to a swelling and tenderness response of 1.

In addition, injected joints will be counted as swollen and tender (ie, swelling and tenderness response of 1) from and including the date of injection up to 52 weeks after injection.

Injected joints are allowed after Week 16 as part of rescue medications.

Dactylitic digits will be identified as follows and the joints will be counted as follows:

- Fingers 2-5: Swelling Distal Interphalangeal Joint x (side), Swelling Proximal Interphalangeal Joint x (side), Swelling Metacarpophalangeal Joint x (side) – if they are in any of the gradings ‘swollen only’ or ‘tender and swelling’ or ‘injected’ then only 1 finger will be added to the swollen joint count.
- Toes 1-5: Swelling Interphalangeal Joint x (side), Swelling Metatarsophalangeal Joint x (side) – if they were in any of gradings ‘swollen’ or ‘tender and swollen’ or ‘injected’ then only 1 toe will be added to the swollen joint count.

The tender joint count (TJC) and swollen joint count (SJC) are weighted joint counts. If there are missing observations in the tender or swollen joint assessments (TJ and SJ, respectively), then the remaining observations will be assessed and weighted by the number of the assessed joints (AJ) as shown below:

$$TJC = n \times \frac{\sum_{i=1}^n TJ}{\sum_{i=1}^n AJ}$$

$$SJC = n \times \frac{\sum_{i=1}^n SJ}{\sum_{i=1}^n AJ}$$

Where n represents the number of total joints.

If a joint is missing at Baseline, then that joint is set to missing throughout the study. If more than 50% of the planned tender joint assessments (ie more than 34) or 50% of the planned swollen joint assessments (ie more than 33) are missing at the time of a given assessment any post-Baseline visit, then no imputation will be done and the total TJC or SJC will be set to missing for that visit.

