The norm-based T-scores for the 2 SF-36 component summary (PCS and MCS) and the 8 domains are standardized with a mean of 50 and a standard deviation (SD) of 10 in the general US population (Maruish, 2011). An individual respondent's score that falls outside the T-score range of 45 to 55 should be considered outside the average range for the US general population. When considering group-level data, a score below 47 should be considered indicative of impaired functioning within that health domain or dimension. Similar to individual respondent

data, group mean scores of 47 or greater should be considered average or above average as compared to the general US population. Higher scores indicate a better health status.

For the calculation of the SF-36 norm-based T-scores for the 8 domains and the PCS and MCS, the scoring software Optum's PRO CoRE (version 1.4) will be used. The software uses updated 2009 U.S. population norms and applies a Full Missing Score Estimation method as follows:

- A health domain score (except the Physical Functioning domain) will be estimated provided that at least 1 non-missing response is available within that domain.
- For the Physical Functioning domain, item response theory will be used to develop a model for estimates of the missing score.
- Regression methods will then be applied to estimate the PCS and MCS on the basis of the available domains.

Change from Baseline at Week 16 in SF-36 PCS score is the 4th endpoint in the sequential testing hierarchy ([Table 4-5](#)).

8.2.1.4 MDA at Week 16

MDA is a state of disease activity deemed a useful target of treatment by both the subject and physician, given current treatment possibilities and limitations. The criteria that need to be met are based on key outcome measures in PsA and are shown below:

- Tender joint count ≤ 1
- Swollen joint count ≤ 1
- PASI ≤ 1 (for subjects with PSO involving at least 3% of BSA at Baseline) or BSA ≤ 3
- PtAAP (VAS) ≤ 15 mm
- PGA-PsA (VAS) ≤ 20 mm
- HAQ-DI ≤ 0.5
- Tender enthesial points ≤ 1 (LEI ≤ 1).

A subject has achieved MDA if 5 or more of the 7 above criteria are fulfilled.

The enthesitis instrument of the study (ie: LEI) will be used to determine whether a subject has ≤ 1 tender enthesial point.

The following rule will be applied for subjects with BSA < 3 at Baseline: Subjects with BSA < 3 at Baseline will always meet the criteria PASI ≤ 1 or BSA ≤ 3 except in the cases where a BSA score > 3 is observed.

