8.3.1.9 Very Low disease activity (VLDA) response

Like MDA, VLDA is a state of disease activity deemed a useful target of treatment by both the subject and physician, given current treatment possibilities and limitations.

A subject is considered as having VLDA if all 7 of the criteria used for MDA and listed in [Section 8.2.1.4](#) are fulfilled.

If any of the 7 MDA criteria is not met, then the subject will be considered as non-responder.

VLDA response will be analyzed at Week 4, 8, 12, 16, 20, 24, 36, 52.

8.3.1.10 Proportion of Subjects with an IGA score of 0 (clear) or 1 (almost clear) AND at least a 2-grade reduction from Baseline in the subset of subjects with psoriatic skin lesions at Baseline

Method for derivation of this variable can be found in [Section 8.2.1.10](#).

The proportion of subjects with an IGA score of 0 (clear) or 1 (almost clear) AND at least a 2-grade reduction from Baseline in the subset of subjects with psoriatic skin lesions at Baseline will be analyzed at Week 4, 8, 12, 16, 20, 24, 36, 52.

For some subjects with BSA $\geq 3\%$ at Baseline, IGA data have not been captured at some post-Baseline visits when BSA $< 3\%$ at those visits. To address that, an additional supportive analysis will be performed in which these subjects will be considered as IGA responders at the respective visit.

In the context of this analysis, observed data for % of BSA affected by PSO will be also analyzed by visit using descriptive statistics.

8.3.1.11 Disease Activity Index for Psoriatic Arthritis (DAPSA) score, state and change from Baseline in DAPSA score

Disease Activity Index for Psoriatic Arthritis (DAPSA) is a composite score of patient global and pain VAS, TJC, SJC and hs-CRP (mg/L) that incorporates a pattern of peripheral arthritis that often is encountered in PsA. DAPSA score will be calculated as follows:

$$DAPSA = SJC + TJC + PGA-Arthritis + PtAAP + hs-CRP$$

where:

- SJC range from 0 to 66
- TJC ranges from 0 to 68
- PGA-Arthritis represents the patient's global assessment of arthritis ranging from 0 to 10 ; 0=best, 10=worst (using the unrounded VAS value that ranges from 0 to 100 mm and dividing this value by 10) ([Section 8.3.1.28](#))
- PtAAP ranging from 0 to 10, 0=best, 10=worst, (unrounded, by dividing the original value by 10)
- hs-CRP in mg/L (no upper limit applied).

DAPSA values will be categorized in the following disease activity states:

- Remission (REM) (DAPSA≤4)
- Low Disease Activity (LDA) (DAPSA >4 and ≤14)

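### MDA and VLDA compare prorated joint and enthesitis counts with 1, so a subject with one affected joint or site and any unassessed one fails that criterion

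*SAP*

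**What the plan says.** **Joint counts (SAP 8.1.1.1).** "Tender and swollen joints are assessed based on the 68 and 66 joints for tenderness and swelling, respectively". When some joints have no assessment, affected joints are divided by assessed joints and multiplied by 68 or 66: "The tender joint count (TJC) and swollen joint count (SJC) are weighted joint counts". A missing joint is an expected and lasting state. "If a joint is missing at Baseline, then that joint is set to missing throughout the study", and "Permanently non-evaluable joints will be considered missing for both tender and swollen joint counts" from the visit of recording onwards. The grading also has a category for joints that temporarily cannot be assessed. A count is set to missing only if more than 34 tender or 33 swollen assessments are missing.

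**Enthesitis (SAP 8.2.1.6).** The LEI has 6 sites and is prorated in the same way if at least 3 are available.

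**MDA (SAP 8.2.1.4).** Three of the seven criteria are "Tender joint count ≤ 1", "Swollen joint count ≤ 1" and "Tender enthesial points ≤ 1 (LEI ≤ 1". Five of seven make a responder. MDA at Week 16 is H5 in Table 4-5.

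**VLDA (SAP 8.3.1.9).** "A subject is considered as having VLDA if all 7 of the criteria used for MDA" are met. VLDA is not in the testing hierarchy.

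**Rounding.** Section 3.1 rounds to 12 decimal places before a threshold comparison. Section 4.2.2.2 (Step 2) rounds to integers only imputed values of variables flagged as integer in Table 4-1. TJC, SJC and LEI are not flagged.

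**The concern.** Proration suits a percentage improvement or a change from Baseline, where scaling both visits matters little. It does not suit a cut-off at the smallest non-zero count. A subject with one tender joint and all 68 assessed scores 1 and meets the criterion. A subject with one tender joint and a replaced or fused joint scores above 1 and fails it. The clinical finding is the same, but the classification depends on a joint that will never be assessable.

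This also sits badly with the SAP's own aims. Section 8.2.1.4 describes the LEI as the means of deciding whether a subject has at most one tender entheseal point. A subject with exactly one tender point and one missing site satisfies that description and fails the numerical criterion. Section 3.1 takes care that floating-point noise does not turn a responder into a non-responder, yet leaves this larger shift in place.

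At stake are the classification for a confirmatory endpoint, the by-visit MDA tables and VLDA. Any error goes in one direction, towards non-response.

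**Working it through.** **1. The plan's own H5 figure.** Inputs from SAP 2.4.1, 2.4.2 and 4.5: MDA 46.3% on bimekizumab and 14.3% on placebo, 420 and 280 subjects, two-sided alpha 0.05.

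- Odds ratio = (0.463/0.537)/(0.143/0.857) = 5.17, as stated.
- Power is above 99%, as stated. With continuity correction, 64 placebo and 96 bimekizumab subjects would already give 99%.

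**2. Score of a subject with exactly one affected joint or site.** With n planned and m unassessed, score = n × 1/(n − m).

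| m | TJC (n = 68) | SJC (n = 66) | LEI (n = 6) |
|---|---|---|---|
| 0 | 1 | 1 | 1 |
| 1 | 68/67 = 1.015 | 66/65 = 1.015 | 6/5 = 1.2 |
| 2 | 1.030 | 1.031 | 6/4 = 1.5 |
| 5 | 1.079 | 1.082 | – |
| 10 | 1.172 | 1.179 | – |
| limit (34, 33, 3) | 2.0 | 2.0 | 2.0 |

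For every m ≥ 1 the score exceeds 1. Zero affected always scores 0 and passes, and two or more always score at least 2 and fail. The proration therefore changes the criterion only for subjects with exactly one affected joint or site, and for them it becomes a requirement of zero.

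**3. Rounding.** To 12 decimals, 68/67 = 1.014925373134, which is still above 1. The integer rule does not reach these variables.

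**4. From criterion to endpoint.** Let c be the number of criteria met on unweighted counts, and k (0 to 3) the number failed only because of proration. MDA is lost when c ≥ 5 and c − k < 5:

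- c = 5 with k ≥ 1
- c = 6 with k ≥ 2
- c = 7 with k = 3

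VLDA is lost when c = 7 and k ≥ 1. One permanently non-evaluable joint can tighten both joint criteria, because it leaves both counts. A hip affects only the tender count, since swelling excludes hips.

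**5. Effect on H5.** As an assumption, let 20% of MDA responders be lost in both arms: 0.463 × 0.8 = 0.370, 0.143 × 0.8 = 0.114, difference 25.6 points instead of 32.0. Power remains above 99%.

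**6. Ceiling on the rate.** The SAP does not give the share of subjects with an unassessed joint or site. If it were 2%, 5% or 10% (assumed), the overall MDA rate could fall by at most 2, 5 or 10 points. The real fall would be smaller, since only subjects with exactly one affected joint or site and a marginal criteria count are reclassified.

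**The case against.** **Section 8.2.2 may allow another reading.** It says that the rules for deriving MDA may differ from those for the individual components, and that some component imputations are not needed for MDA. Section 8.1.1.1 itself speaks of proration as imputation. But Section 8.2.2 goes on to say how many criteria must be known, met or failed. It sets no rule for using raw counts, so the defined TJC, SJC and LEI remain the natural inputs.

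**Proration may be intended.** One tender joint of 67 assessed is not the same data as one of 68, and giving no credit for incomplete data fits the non-responder approach. This has some force for joints that are temporarily unassessable. It has little for a joint that is permanently non-evaluable or missing from Baseline on.

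**The effect is small and common to all arms.** This stands. A reader might infer that an affected subject fails MDA, or that H5 is at risk. The documents support neither: 5 of 7 criteria suffice, the rule is identical in every arm, and H5 has ample power.

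**Integer rounding would not be a clean remedy.** This also stands. One tender joint would still fail with 23 or more unassessed (68/45 = 1.51, rounded to 2), as would one tender site with two missing (6/4 = 1.5, rounded to 2). Rounding would also loosen the cut-off to below 1.5 for multiply imputed values.

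**Timing.** Amendment 3 was written for the Week 52 tables. The Week 16 endpoints belong to the Week 24 analysis, for which treatment codes are released to independent unblinded staff (Section 4.3.1). This limits how a change can be introduced.

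**Conclusion.** The point holds as a defect in a stated rule. For a subject with exactly one tender joint, swollen joint or tender entheseal site and any unassessed one, the corresponding MDA and VLDA criterion fails. That is certain from the formulas and always goes towards non-response.

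The consequence for H5 is limited to subjects whom such a failure takes from 5 or more criteria to fewer than 5. For VLDA one failure is enough, but VLDA is outside the hierarchy. The effect on the MDA rates is probably small. No point estimate can be given, because the SAP reports neither the share of subjects with unassessed joints or sites nor the distribution of criteria met. The power statement rests on the SAP's assumed rates and on an assumed loss of up to 20% of responders in both arms. The correction is worth making because MDA is a confirmatory endpoint and the classification should not depend on an unassessable joint.

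**What to change.** In Section 8.2.1.4, state that the three cut-offs at 1 use the unweighted number of observed tender joints, swollen joints and tender entheseal sites, provided the existing completeness rules are met (no more than 50% of joints missing, at least 3 LEI items available). Refer to this in Section 8.3.1.9 and, for observed values only, in Section 8.2.3. Leave multiply imputed values as they are, and keep the weighted counts for ACR response and change from Baseline.

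If the Week 16 MDA result has already been produced unblinded, keep it and report the corrected derivation beside it as a sensitivity analysis.

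The cost is a short addition to the text, a small programming change and, where it applies, one extra analysis. The downside is that MDA and VLDA rates rise slightly in all arms, and subjects with temporarily unassessed joints are credited on the joints that were observed.
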